7.1.6 Follow up period

All patients must have safety evaluations for 30 days after the last dose of study treatment. In addition, all patients must be followed for the occurrence of Adverse Events and Serious Adverse Events for 30 days after the last dose of study drug. Once an Adverse Event or a Serious Adverse Event is detected, it should be followed until its resolution or until it is judged to be permanent.

Patients lost to follow up should be recorded as such on the eCRF. For patients who are lost to follow-up, the Investigator should show "due diligence" by documenting in the source documents steps taken to contact the patient, e.g., dates of telephone calls, registered letters, etc.

7.2 Assessment types

7.2.1 Disease progression

Disease progression will be documented by a $> 25\%$ increase in spleen length by palpation compared to the on-study nadir **or** by disease symptoms progression based on the Investigator's expert judgment **or** by a significant increase in blood or bone marrow blasts consistently for at least 2 weeks that in the expert opinion of the Investigators indicates progression of disease. Bone marrow biopsies are not required to document progression, however may be performed as clinically indicated and at the discretion of the investigator. If performed, findings should be documented in the eCRF.

7.2.2 Efficacy assessments

Efficacy, beyond clinical response assessment by IWG-MRT, is an exploratory endpoint in this study.

7.2.2.1 Splenic palpation

This assessment will consist of measurement of the spleen length by manual palpation at the end of Cycle 6 (Study Day 169) in comparison to the Cycle1 Day 1 measurement or by change in volume by MRI/CT (see section 7.2.2.3). Patients who have $\geq 50\%$ reduction in spleen length by palpation compared to the initial measurement at Cycle 1 Day 1 will be considered as responders, otherwise they will be considered non-responders by IWG-MRT criteria. Spleen length measurements will be conducted at the start of every cycle in order to exclude disease progression, which is a criterion for premature patient withdrawal (see Section 7.1.5.1).

The edge of the spleen shall be determined by palpation, and measured in centimeters, from the costal margin to the point of greatest splenic protrusion.

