4.1 Description of study design

Phase I/II open label, single institution, study of induction RUXOLITINIB followed by concurrent administration of RUXOLITINIB and PANOBINOSTAT in a 3+3 cohort dose escalation schema in eligible patients with MF (see Figure 4-2). Screening for this study will have a window of 56 days and start on day -84 with signing of informed consent. See Figure 4-1 A and B. Eligible patients will begin induction phase therapy on day -28, receiving single agent RUXOLITINIB PO BID daily for 28 days. The dose of RUXOLITINIB in the induction cycle days -28 to 0 will be the same dose that the patient will receive in the assigned combination cycles. Patients who maintain a platelet count $\geq 50,000/\mu\text{L}$ at Day 1 will then receive concomitant PANOBINOSTAT PO TIW QOW or PO TIW QW depending on the cohort assignment. The induction phase of the Phase I study is not the evaluable phase I component and AEs that are noted in the induction phase will not constitute a dose limiting toxicity (DLT) and patients who do not maintain a platelet count $>50 \times 10^9/\text{L}$ will be removed and will not be able to continue onto the combination drug evaluable phase I period of 28 days and will not be counted in the evaluable phase I cohort for the purposes of dose escalation.

Phase I

The first 28 days of combination therapy will be the evaluable phase I portion of the study. Patients who do not experience a defined DLT in the dose evaluation stage of phase I can remain on study receiving combination drug therapy for a total of 6 cycles (cycles 2-6). See Figure 4-1 A. AEs will continue to be recorded on all patients (phase I and II) receiving combination therapy beyond the first cycle of the study. Dose escalation rules are based on the standard 3+3 design as shown in Figure 4-2.

Note that in this Phase I study, the initial cohort(s) will fix the dose of RUXOLITINIB and escalate the dose of PANOBINOSTAT. Thus, the first endpoint will be to find the MTD of PANOBINOSTAT associated with a fixed dose of 10 mg of RUXOLITINIB. At that point, the dose of PANOBINOSTAT will be fixed at the MTD just mentioned, and RUXOLITINIB will be escalated to 15 mg. The rules of the 3+3 design will govern whether 15 mg is an acceptable dose for RUXOLITINIB in combination with the MTD of PANOBINOSTAT. The rules of the 3+3 design will again be employed to decide on the frequency of administration of PANOBINOSTAT.

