7.2.2.3 MRI/CT

MRI or CT will be performed for the purpose of measuring spleen volume. This will be performed at baseline (screening), C4D1 \pm 1 week, and C6D29/C7D1 \pm 1 week, or when possible when the patient permanently discontinues study treatment, whichever comes first. Patients achieving a 35% reduction in splenic volume will be considered responders, otherwise they will be considered non-responders. These patients will also continue to be assessed by physician palpation of splenic length at the start of each cycle. MRI is the preferred method for obtaining spleen volume data, however, CT scans may be performed at the visits where MRI would be conducted if the subject is not a candidate for MRI, or if MRI

is unavailable. The imaging modality used at baseline (MRI or CT) to assess spleen volume should be kept constant throughout the trial period for a given patient, unless a new contraindication to the use of MRI occurs.

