10.4.2.2 Dose expansion

The cohort of 6 patients at the MTD and/or RPTD will be expanded by an additional 16 patients in order to further assess safety and tolerability. Thus the number of patients treated at the MTD and/or RPTD will be 22, which ensures that there is a 90% chance to detect any AE with a 10% incidence rate among patients treated at the MTD and/or RPTD. During this phase of the study, further defining of the biological activity of this combination will be explored. The primary endpoint of this portion of the trial is response rate by IWG-MRT criteria. We hypothesize a response rate of >40% in treated patients at C6D28 will constitute a positive primary endpoint. A positive response by IWG-MRT criteria includes SD, CI, PR, or CR. Since preclinical studies suggest a synergistic effect of the two agents in combination, we would expect a spleen response rate (>35% reduction in spleen volume by MRI or >50% reduction in palpable spleen) of >30% as was assumed in the COMFORT study. Since the proportion of patients obtaining this efficacy endpoint was 42%, we will have a target response for this secondary endpoint of >50%, and this will be reported in a descriptive manner.

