10.6.5 To evaluate changes in packed red blood cell transfusion dependence

The proportion of patients who are transfusion dependent, as well as, the proportion of patients whose transfusion status (dependent or independent) changed (from dependent to independent or vice versa - (Gale 2011)) at each cycle will be tabulated with summary statistics.

- A patient will be defined as transfusion dependent at baseline if he or she received 2 or more units of red blood cell products during the 12 weeks prior to first study treatment administration
- New onset of transfusion dependence will be defined as the use of 2 or more units of red blood cell products during the last 12 weeks prior to end of study for patients who were not transfusion dependent at Baseline
- New transfusion independence will be defined as no use of red blood cell products during the last 12 weeks prior to the end of study for patients who met the definition of transfusion dependence at baseline.

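### The combined spleen response mixes two baselines: palpation is counted from Cycle 1 Day 1, after 28 days of ruxolitinib, and MRI/CT volume from the screening scan before it

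*Combined protocol and SAP*

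**What the plan says.** **Timeline.** Section 4.1: "Screening for this study will have a window of 56 days and start on day -84 with signing of informed consent". After that, "Eligible patients will begin induction phase therapy on day -28, receiving single agent RUXOLITINIB PO BID daily for 28 days". Section 6.1.1 gives the first panobinostat dose on Cycle 1 Day 1 (C1D1). C1D1 is thus both the end of the ruxolitinib-only month and the start of the combination.

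**Palpation.** Section 7.2.2.1 judges spleen length at the end of Cycle 6 "in comparison to the Cycle1 Day 1 measurement or by change in volume by MRI/CT". Patients with a fall of 50% or more "compared to the initial measurement at Cycle 1 Day 1 will be considered as responders"; the others are non-responders under the IWG-MRT criteria.

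**Imaging.** On the scans, section 7.2.2.3 says: "This will be performed at baseline (screening), C4D1", with a further scan at the end of Cycle 6. No scan is listed at C1D1. The rule is: "Patients achieving a 35% reduction in splenic volume will be considered responders, otherwise they will be considered non-responders".

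**Combined rate.** Section 10.4.2.2 defines spleen response as ">35% reduction in spleen volume by MRI or >50% reduction in palpable spleen", sets a target above 50%, and reports it descriptively.

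**Statistics section.** Sections 10.6.1 (palpation) and 10.6.2 (volume) both refer to change from baseline, and neither gives a date for it.

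**The concern.** The two halves of the either-or rule measure different things. Palpation from C1D1 asks what happened to the spleen after panobinostat was added. Volume from screening asks what the whole regimen did, ruxolitinib month included. A rate that pools them describes neither quantity, and a patient can pass one part and fail the other only because of the starting date.

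The two thresholds are also meant to be interchangeable: section 1.3.3 treats a 35% fall in volume as roughly a 50% fall in palpable length. That pairing makes sense only if both falls start from the same point.

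At stake are the reading of the spleen rate against its target, the palpation response rates, and which patients are labelled clinical improvement (CI) rather than stable disease (SD).

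**Working it through.** The plan states no figure that depends on this choice, so there is none to reproduce. The check compares the definitions and works out what the thresholds imply.

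**Inputs**
- Palpation threshold: 50% fall in length from C1D1 (7.2.2.1).
- Volume threshold: 35% fall from the screening scan (7.2.2.3).
- Between the two baselines: 28 days of ruxolitinib alone (4.1), and about 84 days in calendar time if the scan is done when screening opens on day -84.
- Fall in palpable length during induction, *s*, and fall in volume during induction, *v*: **assumptions**. The documents give no 28-day spleen figure.

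**Palpation, expressed from screening.** Let length at screening be 1. At C1D1 it is 1 − s. A 50% fall from there leaves 0.5(1 − s), so the required fall from screening is 1 − 0.5(1 − s).

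**Volume, expressed from C1D1.** A 35% fall from screening leaves 0.65 of a volume that was 1 − v at C1D1, so the further fall needed after C1D1 is 1 − 0.65/(1 − v).

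| Assumed fall in induction | Palpation: fall needed from screening | Volume: further fall needed after C1D1 |
|---|---|---|
| 0% | 50% | 35% |
| 10% | 55% | 27.8% |
| 20% | 60% | 18.8% |
| 30% | 65% | 7.1% |

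**One patient.** Length is 20 cm at screening, 14 cm at C1D1 and 8 cm at the end of Cycle 6. From screening the fall is 12/20 = 60%, a response. From C1D1 it is 6/14 = 43%, a non-response.

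**Direction.** If s ≥ 0, then 1 − 0.5(1 − s) ≥ 50%. Everyone who responds by palpation from C1D1 would also respond from screening, but not the reverse. The either-or rate as now defined therefore cannot exceed the rate with a pre-induction baseline for both measures. If the spleen grows in induction the sign flips: for s = −10%, the fall needed from screening is 1 − 0.5(1.10) = 45%.

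**CI against SD.** In Table 4-1 the 50% spleen route to CI requires at least 10 cm at baseline. A spleen that goes from 12 cm at screening to 9 cm at C1D1 qualifies for that route on the first baseline and not on the second. A patient who misses CI for this reason, and has not progressed, is SD. Sections 10.4 and 10.4.2.2 count SD as response, so the primary outcome is the same.

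**The case against.** The strongest reply is that little depends on this. The endpoint is secondary and descriptive, section 10.8 plans no testing or power for secondary variables, and section 10.6.2 restates the target above 50% for volume alone. Under an either-or rule with the correspondence in section 1.3.3, most palpation responders should also meet the volume criterion, so the combined rate should lie close to the volume rate. All of this stands and limits the consequence. It does not settle which change the rate describes.

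C1D1 is also a defensible baseline for what panobinostat adds. But the plan gives no such rationale, and the scans cannot follow it because none is taken at C1D1.

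A reader might infer more than the documents support:

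- *That the primary IWG-MRT rate is distorted.* Moving patients between CI and SD does not change it. Section 7.2.2.1 sets C1D1 for the response threshold, and nothing in the plan says that progression is counted from C1D1.
- *That the comparison with the 42% benchmark fails.* That figure is a volume response (section 1.3.3), and volume here already starts from a pre-induction scan. Only the palpation component is out of line with it.
- *That transfusion dependence adds a third conflicting baseline.* Section 10.6.5 counts units "during the 12 weeks prior to first study treatment administration", but this is a separate exploratory objective. Its start date is also unclear, since section 7.2.5.6 ties the first dose of study drug to C1D1.
- *That every screening value is ruxolitinib-free.* Sections 5.1 and 5.2 let suboptimal responders enter without stopping ruxolitinib, reduced to 10 mg BID. For them s could be zero or negative.

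**Conclusion.** The inconsistency is real: sections 7.2.2.1 and 7.2.2.3 use baselines on opposite sides of the ruxolitinib month, section 10.4.2.2 pools them, and section 10.6 does not reconcile them. For assumed induction falls of 10% to 30%, the palpation criterion is a 55% to 65% fall on the screening scale instead of 50%. The effect on the response rate itself cannot be computed, because the documents give neither the induction change nor the overlap of the two criteria.

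The reach is limited to the descriptive spleen response, the palpation response rates and the CI-against-SD split. The combined rate tends to be understated, provided the spleen does not grow in induction. No hypothesis test or sample size depends on it, and the CI-against-SD split does not move the primary rate.

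**What to change.** - In sections 7.2.2.1, 10.4.2.2 and 10.6, name one pre-induction baseline for both spleen measures: the last palpation before the first induction dose of ruxolitinib, and the screening scan.
- Report palpation change from C1D1 as a separate add-on analysis.
- Report patients who enter on continuing ruxolitinib separately, because their screening value is not ruxolitinib-free.

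**Cost.** Wording only. Palpation is already recorded at screening (7.1.2, 7.1.2.3) and at every visit (7.2.4), and the screening scan is already required. A common C1D1 baseline would instead need an added scan. The downside is that a pre-induction baseline credits shrinkage from ruxolitinib alone to the regimen; the C1D1 add-on analysis lets the reader see how much. Palpation and scan may still fall on different days of the 56-day screening window, but both precede induction.

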7.2.2.2 Disease symptom assessments/MPN-SAF

Evaluation of constitutional symptoms (weight loss $>10\%$ of the baseline value in the year preceding C1D1, unexplained fever, or excessive night sweats persisting for more than 1 month) should be performed at baseline, and the start of every cycle. The MPN-SAF validated symptom assessment tool questionnaire will be used to gauge baseline MF symptoms and changes in symptoms with treatment. See Appendix 3.

7.2.2.3 MRI/CT

MRI or CT will be performed for the purpose of measuring spleen volume. This will be performed at baseline (screening), C4D1 \pm 1 week, and C6D29/C7D1 \pm 1 week, or when possible when the patient permanently discontinues study treatment, whichever comes first. Patients achieving a 35% reduction in splenic volume will be considered responders, otherwise they will be considered non-responders. These patients will also continue to be assessed by physician palpation of splenic length at the start of each cycle. MRI is the preferred method for obtaining spleen volume data, however, CT scans may be performed at the visits where MRI would be conducted if the subject is not a candidate for MRI, or if MRI

is unavailable. The imaging modality used at baseline (MRI or CT) to assess spleen volume should be kept constant throughout the trial period for a given patient, unless a new contraindication to the use of MRI occurs.

7.2.2.4 Bone marrow biopsy

The bone marrow biopsy and aspirate should be collected, processed, stained, and assessed by an experienced hematopathologist using his/her Institutional standards. Bone marrow fibrosis should be graded using the European consensus grading system (Tefferi 2006).

The bone marrow biopsy and/or aspirate will be collected at screening and C6D29 (+/- 1 week). The screening bone marrow biopsy and/or aspirate can be omitted if a sample was collected within the previous 3 months from study treatment, and the subject has not been on any therapy for MF during the intervening period, and all data from this collection can be entered into the eCRF for this study, with explanation as to the origin of the data. In the extension phase of the study the bone marrow biopsy and aspiration will be performed when clinically indicated and not more frequent than every 6 months.

7.2.3 Safety assessments

Safety will be monitored by assessing and collecting the adverse events at every visit. For details on AE collection and reporting, refer to Section 8.

7.2.4 Physical examination

A complete physical examination will be performed, as noted in Appendix 2 (+/- 3 days up until the end of cycle 6 and then +/- 7 days for C7 and beyond), and must include at a minimum measurement of spleen length, assessed by palpation and measured in centimeters using a soft ruler, from the costal margin to the point of greatest splenic protrusion at every visit.

Significant findings that were present prior to the signing of informed consent must be included in the Relevant Medical History/Current Medical Conditions page on the patient's eCRF. Significant new findings that begin or worsen after informed consent is signed must be recorded on the Adverse Event within the eCRF.

7.2.4.1 Vital signs

Vital signs (blood pressure, pulse, respiratory rate and body temperature) will be collected at every visit (+/- 3 days up until the end of cycle 6 and then +/- 7 days for C7 and beyond). Vital signs should be taken with the patient in the sitting position after 5 minutes of rest. Body temperature may be measured orally or via ear.

7.2.4.2 Height and weight

Height in centimeters (cm) should be measured at screening only. Body weight in kilograms (to the nearest 0.1 kilogram [kg], without shoes) should be measured at every visit (+/- 3 days up until the end of cycle 6 and then +/- 7 days for C7 and beyond).

7.2.4.3 Performance status

The performance status will be assessed according to the ECOG performance status scale (Table 7-3), at time points specified in Appendix 2 (+/- 3 days up until the end of cycle 6 and then +/- 7 days for C7 and beyond).

Table 7-3 ECOG performance status

Grade	ECOG
0	Fully active, able to carry on all pre-disease performance without restriction
1	Restricted in physically strenuous activity but ambulatory and able to carry out work of a light or sedentary nature, e.g., light house work, office work
2	Ambulatory and capable of all self-care but unable to carry out any work activities. Up and about more than 50% of waking hours
3	Capable of only limited self-care, confined to bed or chair more than 50% of waking hours
4	Completely disabled. Cannot carry on any self-care. Totally confined to bed or chair
5	Dead

7.2.5 Laboratory evaluations

The laboratory evaluations will be performed by a local lab according to the visit schedule in Appendix 2 (+/- 3 days up until the end of cycle 6 and then +/- 7 days for C7 and beyond).

Abnormal laboratory values or test results constitute as an AE only if they induce clinical signs or symptoms, and are considered clinically significant (i.e., require dose modification and/or interruption of study drug, lead to clinical symptoms, cause study discontinuation or constitute in and of itself an SAE) or require therapy. These events should be recorded on the eCRF. If the administration of PANOBINOSTAT and/or RUXOLITINIB is delayed/modified due to unacceptable toxicities (see Section 6.2.7), re-evaluation should be performed prior to the next study treatment at a minimum.

All available labs should be performed and results of Hematology reviewed prior to administration of study drug. More frequent examinations may be performed at the Investigator's discretion if medically indicated; results should be recorded on the Unscheduled Visit eCRF.

Baseline labs may be repeated, if needed, to obtain acceptable values before the patient would screen fail. Laboratory tests should be collected and analyzed on the scheduled day appendix 2, or +/- 3 days up until the end of cycle 6 and then +/- 7 days for C7 and beyond.

7.2.5.1 Hematology

Hematology tests include the following parameters:

- Complete blood count (CBC) consisting of total white blood cell count (WBC) with differential (total neutrophil including bands, lymphocyte, monocyte, eosinophil, basophils counts, and blasts)
- Hemoglobin
- Hematocrit

- Platelet count

7.2.5.2 Biochemistry

Biochemistry includes the following parameters:

- Urea or blood urea nitrogen (BUN), creatinine, sodium, potassium, glucose, total calcium (corrected for serum albumin) or ionized calcium, albumin, total protein, total bilirubin (direct and indirect if total bilirubin is $>$ ULN), lactate dehydrogenase (LDH), alkaline phosphatase, AST/SGOT, ALT/SGPT, phosphorous, magnesium, and uric acid.

Potassium, calcium, magnesium, and/or sodium supplements may be given to correct values that are $<$ LLN. Post-correction values must not be deemed to be a clinically significant abnormality prior to patients being dosed.

7.2.5.3 Coagulation

The coagulation profile includes a prothrombin time (PT)/International Normalized Ratio (INR), and partial thromboplastin time (PTT).

The coagulation profile should be repeated as clinically indicated and these results should be recorded on the Unscheduled Visit eCRF.

7.2.5.4 Thyroid function tests

TSH and free thyroxine (FT4) will be evaluated at time points specified in Appendix 2.

7.2.5.5 Urinalysis

Urinalysis tests include a macroscopic exam, including assessment of protein, glucose, blood, and specific gravity at timepoints specified in Appendix 2. Should an abnormality be noted in the macroscopic exam, a microscopic examination should also be performed, including assessment of WBC/HPF, RBC/HPF, and documentation of any additional findings.

If the administration of oral PANOBINOSTAT is delayed/modified due to unacceptable renal toxicities, re-evaluation should be performed prior to the next study treatment at a minimum.

